	
targets and will be performed after cycle 2, then after every other cycle.
 
 • A subject will be defined as a responder if CR/PR is observed at any time of the treatment • Clinical response will be seen if stable disease and decrease in tumor markers by $\geq 50\%$ or CR of bone marrow. • Time to progression, defined as the period from the start of the treatment until the criteria for progression are met taking as reference the screening measurements • Comparisons of ORR and PFS for the first and second cohorts of 100 patients (i.e., those who enroll prior to versus after the implementation of Amendment 3.0, respectively) will be performed. 
Safety Measures: Secondary objectives
 
 • Safety analysis will be conducted on all subjects who have received at least one dose of therapy, and will include the frequency of all reported adverse events and laboratory abnormalities as well as frequency of dose interruptions, dose reductions and treatment discontinuation.
STATISTICS/SAMPLE SIZE ESTIMATE	
200 evaluable subjects
 
Patients who enroll following implementation of Amendment 3.0 (second cohort of 100 patients) will have their tumor biopsies analyzed using an updated Drug Prediction Report (Appendix III). Overall Response Rate (ORR) and Progression Free Survival (PFS) for this group will be compared to those of the first 100 patients who received treatment based upon the original Drug Prediciton Report and Pharmacopeia Library.

TABLE OF PROCEDURES AND ASSESSMENTS

Procedure	Screening	Cycle 1 Day 1	Cycle 1 Day 8	Cycle 1 Day 15	Cycle 1 Day 22 (if applicable)	Subsequent Cycles Day 1	Off Therapy/ 30 Day Follow-up
Informed consent	X						
Demographics	X						
Medical history	X	X	X	X	X	X	
Baseline Symptom Form	X	X					
Concurrent meds	X	X				X	X
Physical exam	X	X	X	X	X	X	X
Vital signs	X	X	X	X	X	X	X
Height	X	X				X	
Weight	X	X				X	X
Karnofsky or Lansky play score	X	X		X		X	X
CBC w/diff,	X	X	X	X	X	X	X
Serum chemistry *	X	X		X		X	X
Tumor Markers **	X	X				X	X
Adverse events			X	X	X	X	X
Surgical resection &/or diagnostic biopsy	X						
MRI or CT***	X						
MIBG/PET ***	X						
Bone Marrow (any subject suspected to have BM disease) ^	X						
B-HCG	X						
EKG (as indicated)		X					

* Serum electrolytes, BUN, Creatinine, Bilirubin, ALT, AST

**LDH and/or Specific Tumor Markers for defined disease (if available)

***Type of scan as indicated for disease type

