2.2 Secondary Objectives

- ◆ To determine the activity of treatments chosen based on:
 - Overall response rate (ORR)
 - Progression free survival (PFS)
- ◆ To continue to evaluate the safety of allowing a molecular tumor board to determine individualized treatment plans
- ◆ (Voluntary) To explore the relationship between tumor phenotype/genotype and response by permitting use of tumor tissue in a correlative biologic study
- ◆ To compare PFS interval to PFS intervals of previous chemotherapy regimens since relapse for each subject.
- ◆ Sub analysis examination of disease types.

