4.2 Exclusion Criteria

1. Subjects who have received any cytotoxic chemotherapy within the last 7 days prior to biopsy
2. Subjects who have received any radiotherapy to the primary sample site within the last 14 days (radiation may be included in treatment decision after biopsy).
3. Subjects receiving any investigational drug concurrently.
4. Subjects with uncontrolled serious infections or a life-threatening illness (unrelated to tumor)
5. Subjects with any other medical condition, including malabsorption syndromes, mental illness or substance abuse, deemed by the Investigator to be likely to interfere with the interpretation of the results or which would interfere with a subject's ability to sign or the legal guardian's ability to sign the informed consent, and subject's ability to cooperate and participate in the study

Additional criteria:

Subjects willing to participate in the correlative biologic studies will sign an additional consent form to provide additional tumor tissue.

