6.2 Concomitant Medications and Treatments

All intercurrent medical conditions will be treated at the discretion of the Investigator according to acceptable community standards of medical care. All concomitant medications and treatments will be documented on the appropriate case report form.

The following medications are not permitted during the trial:

- Any cytotoxic chemotherapy
- Any other investigational treatment
- Any other systemic anti-neoplastic therapy including, but not limited to, immunotherapy, hormonal therapy, targeted therapies, anti-angiogenic therapies, or monoclonal antibody therapy

The following medications/treatments may be administered as follows:

- Any radiotherapy administered with palliative intent/pain control or recommended by tumor board as part of therapeutic regimen for best patient care.
- Prophylactic filgrastim, pegfilgrastim or oprelvekin; these hematopoietic growth factors may be administered according to ASCO, ASH, or institutional guidelines to treat an established cytopenia
 - If subject experiences a prolonged neutropenia greater than 72 hours during Cycle 1; consider using filgrastim or pegfilgrastim during all subsequent cycles.

- Erythropoietin, blood products, anti-emetics, steroids, and transfusions may be administered at the discretion of the Investigator based on established criteria.

7 Efficacy Assessments

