7.3 Response Criteria

Overall response rate (ORR) in subjects with radiologically assessable disease will be determined by CT or MRI by cross-sectional imaging, MIBG/PET scans, and/or bone marrow assessment.

Response Assessment: Each subject will be classified according to their “best response” for the purposes of analysis of treatment effect. Best response is determined from the sequence of the objective statuses described below.

Response Criteria for Subjects with Solid Tumors: This study will use the (RECIST) Response Evaluation Criteria in Solid Tumor (version 1.1) from the NCI[44]. Key points are that a maximum of 5 target lesions are identified and that changes in the *largest* diameter (uni-dimensional measurement) of the tumor lesions are used in the RECIST v1.1 criteria.

- **Measurable disease:** The presence of at least one lesion that can be accurately measured in at least one dimension with the longest diameter at least 10 mm (CT scan slice thickness no greater than 5 mm). The investigator will identify up to 5 measurable lesions to be followed for response. Previously irradiated lesions must demonstrate clear evidence of progression to be considered measurable.
- Serial measurements of lesions are to be done with CT or MRI, using the same method of assessment is to be used to characterize each identified and reported lesion at baseline and during follow-up.

- Quantification of Disease Burden The sum of the longest diameter (LD) for all target lesions will be calculated and reported as the disease measurement.
- **Complete Response (CR):** Disappearance of all target and non-target lesions.
- **Very Good Partial Response (VGPR):** Greater than 90% decrease of the disease measurement for CT/MRI lesions, taking as reference the disease measurement done to confirm measurable disease at study entry. Non-target CT/MRI lesions stable to smaller in size.
- **Partial Response (PR):** At least a 30% decrease in the disease measurement, taking as reference the disease measurement done to confirm measurable disease at study enrollment. No new lesions or progression of any non-target measurable lesion.
- **Stable Disease (SD):** Neither sufficient decrease to qualify for PR or sufficient increase to qualify for PD from study entry.

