- **Progressive Disease (PD):** At least a 20% increase in the sum of the disease measurements for measurable lesions, taking as reference the smallest disease measurement recorded since the start of treatment (nadir), and minimum 5 mm increase over the nadir or the appearance of one or more new lesions.

Response Criteria for Subjects with Bone Marrow Disease:

- Those subjects with morphologic evidence of disease by routine H and E staining (NSE staining only is not evaluable) will be evaluable to assess bone marrow response.
- **Complete response:** No tumor cells detectable by routine morphology on two consecutive bilateral bone marrow aspirates and biopsies done at least three weeks apart after study entry.
- **Progressive disease:** Tumor seen on morphology on two consecutive bone marrows done at least three weeks apart in subjects who had NO tumor in bone marrow at study entry. (Note: Subject may be declared as progressive disease in bone marrow after only one diagnostic bone marrow at the discretion of the treating physician after discussion with the study chair.)
- **Stable disease:** Persistence of an amount of tumor in the bone marrow by morphology that does not meet criteria for either complete response or progressive disease.

Response Criteria for Subjects with MIBG or PET Positive Lesions

- Subjects who have a positive MIBG or PET scan at the start of therapy will be evaluable for MIBG or PET response. All MIBG's and PET scans will be performed at the research institution and then centrally reviewed.
- **Complete response** = complete resolution of all positive lesions
- **Partial response** = resolution of at least one positive lesion, with persistence of other MIBG positive lesions.
- **Stable disease** = no change in scan in number of positive lesions (includes subjects who have same number of positive lesions but decreased intensity)
- **Progressive disease** = Development of new positive lesions

The intensity of MIBG uptake is not to be considered in the above institutional evaluation.

Duration of response:

Duration of response is defined as the period of time from when measurement criteria are met for complete response (CR) or partial response (PR), whichever is first recorded, until the first date that recurrent or progressive disease (PD) is objectively documented (taking as reference for PD the smallest measurements recorded since the treatment started).

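### No response rule covers lesions irradiated on study, so shrinkage after palliative radiotherapy outside the tumor board's regimen can be counted as CR/PR and raise ORR

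*Combined protocol and SAP*

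**What the plan says.** Two kinds of radiotherapy are open to subjects on study. Section 6.2 lists as permitted "Any radiotherapy administered with palliative intent/pain control or recommended by tumor board as part of therapeutic regimen for best patient care". Section 4.2 confirms, for the board's plan, that "radiation may be included in treatment decision after biopsy". Because radiotherapy is not a prohibited treatment, it does not take a subject off therapy under Section 11.1.

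Response is defined in Section 7.3 and in the Synopsis (Criteria for Evaluation):

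- CT/MRI burden: "The sum of the longest diameter (LD) for all target lesions will be calculated and reported as the disease measurement".
- CT/MRI PR: "At least a 30% decrease in the disease measurement, taking as reference the disease measurement done to confirm measurable disease at study enrollment", with no new lesion and no progression of a non-target measurable lesion.
- MIBG/PET PR: "resolution of at least one positive lesion, with persistence of other MIBG positive lesions".
- Responder: "A subject will be defined as a responder if CR/PR is observed at any time of the treatment".

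The only sentence on irradiated lesions concerns baseline: "Previously irradiated lesions must demonstrate clear evidence of progression to be considered measurable". Section 12.4 plans ORR with exact 95% confidence intervals and PFS by Kaplan-Meier, and does not mention radiotherapy. Section 8 adds a comparison of ORR and PFS between the 100 patients enrolled after Amendment 3.0 and the first 100. The secondary objective in Section 2.2 is "To determine the activity of treatments chosen based on" ORR and PFS.

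**The concern.** The baseline sentence shows that the authors regard radiation as compromising a lesion for measurement. Nothing carries that caution into follow-up. No passage excludes a lesion irradiated on study, calls it not evaluable, censors the subject at radiotherapy or plans a sensitivity analysis. If the rules are applied literally, a lesion treated for pain stays in the sum, or in the count of positive lesions, and its local response can make the subject a responder.

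ORR is meant to describe the activity of the treatments the board chose. Palliative radiotherapy given outside that choice is not one of them. The two cohorts of 100 are sequential and not randomised, so a shift in radiotherapy practice between them could also appear as an effect of the new Drug Prediction Report.

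**Working it through.** **The plan's own figure.** The documents give no figure on this point. The one stated design calculation is the two-stage feasibility rule (5/9, then 10/16). It reproduces: the probability of stopping at stage 1 is 0.7461 at 50% and 0.1657 at 75% (stated 0.746 and 0.166). Exact type I error is 0.0878 and power 0.7532. This point does not depend on it.

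**Can radiation alone give a PR on CT/MRI?** Let w be the irradiated lesion's share of the baseline sum and s its fractional shrinkage, with other lesions unchanged. PR needs w × s ≥ 0.30.

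| Shrinkage s | Smallest share w = 0.30/s |
|---|---|
| 50% | 60% |
| 75% | 40% |
| 100% | 30% |

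- Targets of 50 and 20 mm, with the 50 mm lesion halved: the sum goes from 70 to 45 mm, a fall of 25/70 = 35.7%. This is PR.
- Five equal lesions, one shrinking 75%: 0.20 × 0.75 = 15%. This is SD.

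So conversion is possible but not automatic. It is easiest when the irradiated lesion is the only target.

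**MIBG/PET.** Clearance of one positive lesion is enough for PR, however many persist. There is no share condition, so this criterion is the more exposed.

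**Size for ORR.** Let p be the true ORR, f the fraction irradiated on a target lesion outside the board's regimen, and q the fraction of irradiated non-responders converted. Only non-responders can be converted, so

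observed ORR = p + (1 − p) × f × q.

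The documents give neither f nor q. Assumed: f = 5-20%, q = 30-50%. For p, the Rationale (Section 1.2) gives 10-35% in relapsed neuroblastoma. It is used here only to set a scale.

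| p | Low: f = 5%, q = 30% | High: f = 20%, q = 50% |
|---|---|---|
| 10% | 0.90 × 0.015 = 1.35 points | 0.90 × 0.10 = 9.0 points |
| 35% | 0.65 × 0.015 = 0.98 points | 0.65 × 0.10 = 6.5 points |

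**Cohort comparison.** If f is 5% in one cohort and 20% in the other, with q = 50% and the same true ORR, the spurious difference is (1 − p) × 0.15 × 0.5. That is 6.75 points at p = 10% and about 4.9 points at p = 35%. If use is equal, the difference is zero.

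**PFS.** Section 7.3 gives two references for progression. The PD definition uses the smallest sum since the start of treatment, with a 20% rise and at least 5 mm. The progression-free survival paragraph uses the screening measurements. Take the 50 + 20 mm case with the larger lesion irradiated to 25 mm:

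- Reference nadir: the nadir is 45 mm and PD falls at 1.2 × 45 = 54 mm, after 9 mm of growth elsewhere. Without radiation, PD falls at 1.2 × 70 = 84 mm, after 14 mm. PD comes earlier.
- Reference screening: PD falls at 84 mm, which from 45 mm needs 39 mm of growth. PD comes later.
- Reference nadir, but with the other lesion growing 14 mm in the same interval as the shrinkage: the sum is 45 + 14 = 59 mm, below 70, so there is no PD. Without radiation it would be 84 mm and PD.

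The sign therefore depends on the reference and on timing. A new lesion is PD in every case.

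**The case against.** The best reply has four parts.

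- **Retention is inferred.** The documents do not say that irradiated lesions are kept. That follows from summing all target lesions and from silence. Section 7.3 also adopts RECIST 1.1 by citation and lists only key points, and the full criteria are not in the documents. This stands: the supportable wording is that such shrinkage can be counted, not that it is.
- **Board-recommended radiotherapy is part of the regimen.** The objective concerns treatments chosen, and Sections 4.2 and 6.2 let the board choose radiation. A reader might infer that all radiation shrinkage is wrongly credited to the drugs. The documents do not support that. The misattribution is confined to palliative radiotherapy outside the board's plan.
- **PFS.** A reader might infer that PFS is inflated along with ORR. The example above shows that it can move either way, and the two progression references are not reconciled.
- **Consequences are limited.** ORR and PFS are secondary and unpowered. The same rule applies to both cohorts, so the comparison is distorted only if radiotherapy use differs. Concomitant treatments are recorded and scans are sent to the coordinating center, so a later sensitivity analysis is probably feasible. This limits the severity. It does not remove the upward bias in ORR when the stated rules are followed.

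**Conclusion.** The concern holds in limited form. As written, the response rules can turn shrinkage or clearance after palliative radiotherapy into CR/PR. The bias in ORR can only be upward, since no rule works against it. Its size cannot be known from the documents. The range of about 1.4 to 9 points at a true ORR of 10%, and about 1 to 6.5 points at 35%, rests wholly on the assumed f and q. It would be near zero if palliative radiotherapy to target lesions is rare. The between-cohort ORR comparison is at risk only if radiotherapy use differs. No direction can be claimed for PFS. The primary feasibility test is untouched. This is a minor point that is worth fixing because the fix is cheap.

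**What to change.** This is a change to the analysis only. Who may be irradiated, and when, stays as it is. State in Sections 7.3 and 12.4:

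1. From the date of palliative radiotherapy, the irradiated lesion (CT/MRI or MIBG/PET) cannot contribute to a new CR or PR.
2. Response is then judged on the non-irradiated lesions, with baseline and nadir sums recalculated without the irradiated one.
3. Responses documented before radiotherapy stand.
4. Subjects whose only lesion was irradiated stay in the ORR denominator as non-responders, unless they had already responded. Dropping them would itself raise ORR.
5. Record the field and date of radiotherapy, and whether the board recommended it. Report use by cohort.
6. Show ORR and PFS with and without irradiated subjects, including those given board-recommended radiotherapy. Read this as sensitivity only: radiotherapy is a post-baseline event, so removing these subjects may select on prognosis.

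The two progression references in Section 7.3 must be reconciled before any PFS sensitivity analysis can be interpreted.

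The cost is a short paragraph in each section, a small addition to the case report form (concomitant treatments are already captured under Section 6.2) and a slightly lower reported ORR.

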- x. Ethesioneuroblastoma (At relapse after standard of care therapy and/or non- responsive/progressive to accepted curative chemotherapy).
- xi. Neuroendocrine tumors (At relapse after standard of care therapy and/or non- responsive/progressive to accepted curative chemotherapy).
- xii. Desmoplastic small round cell tumor (At relapse after standard of care therapy and/or non- responsive/progressive to accepted curative chemotherapy).
- xiii. Melanoma (At relapse after standard of care therapy and/or non- responsive/progressive to accepted curative chemotherapy).

2. Subjects must be age \geq 12 months at enrollment
3. Subjects must be age \leq 21 years at initial diagnosis
4. Subjects must have measurable disease as defined by RESIST v1.1 at the time of biopsy and tumor must be accessible for biopsy. Tumor samples submitted for analysis must contain $>50\%$ viable tumor tissue to qualify. In addition, subjects with disease confined to the bone marrow are eligible to enroll if the degree of marrow involvement is expected to be $>50\%$.
Note: Subjects who are expected to have no evidence of disease after surgical removal of their tumor are still eligible for this trial if their disease would normally require adjuvant chemotherapy treatment after surgery despite NED status.
5. Current disease state must be one for which there is currently no known effective therapy
6. Specimens will be obtained only in a non-significant risk manner and not solely for the purpose of investigational testing.
7. Lansky or Karnofsky Score must be ≥ 50
8. Subjects without bone marrow metastases must have an ANC $> 750/\mu\text{l}$ to begin treatment.
9. Subjects with CNS disease currently taking steroids must have been on a stable dose of steroids for 2 weeks prior to their biopsy and must not have progressive hydrocephalus at enrollment.
10. Adequate liver function must be demonstrated, defined as:
 - a. Total bilirubin $\leq 1.5 \times$ upper limit of normal (ULN) for age AND
 - b. ALT (SGPT) $< 10 \times$ upper limit of normal (ULN) for age
11. A negative serum pregnancy test is required for female participants of child bearing potential (≥ 13 years of age or after onset of menses)

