5.2 Screening

The Investigator is responsible for keeping a record of all subjects screened for entry into the study and subsequently excluded.

The following screening procedures must be performed within 21 days (14 days preferred) prior to date of biopsy*. Studies must be done *after* last previous treatment for malignancy:

1. Signed informed consent form. All subjects (or subjects' legal representatives) must provide written informed consent before any study specific assessments may be performed. Signed informed consent form for voluntary participation in correlative biologic analysis;
2. Complete medical and surgical history, including documentation of the evidence of malignancy and prior treatments for cancer. Include all other pertinent medical conditions and a careful history of all prior medical treatments;
3. Demographics;
4. Physical examination (including height and weight), noting all abnormalities and sites of palpable neoplastic disease;
5. Vital signs, including temperature, pulse rate, and blood pressure;
6. Karnofsky Performance status/Lansky Play status (Appendix I);
7. Complete Screening Baseline Symptom form;
8. CBC with differential;
9. Serum electrolytes (sodium, potassium, chloride, bicarbonate), blood urea nitrogen (BUN), creatinine, albumin, Bilirubin, ALT, and AST;
10. LDH and/or Specific Tumor Markers for defined disease (if available);
11. Serum pregnancy test for female subjects of child bearing potential (onset of menses or \geq 13 years of age);
12. CT or MRI of measurable disease sites (as indicated for tumor type);
13. Solid tumor biopsy for "Primary Sample" with remaining tumor tissue used in correlative biologic studies handled per section 9.3 and submitted per Appendix II.

For subjects that cannot provide a solid tumor biopsy; a bone marrow core biopsy sample will replace the solid tumor sample as the "Primary Sample." Bone Marrow must have adequate tumor (defined as >50% tumor) in order to qualify as "Primary Sample."

***NOTE: If standard-of-care sample collection occurred within 12 weeks prior to enrollment and after last previous treatment for malignancy, and frozen sample remains, a subject may enroll using previously collected samples. Samples must additionally have been snap frozen within 20 minutes of collection and kept in a -70/-80 freezer.**

14. Concomitant medications/therapies including documentation of steroid use and dose;
15. Confirmation of inclusion and exclusion requirements.

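### CNS lesions are scored by size alone while steroid dose may change on study, so shrinkage after a steroid increase would count as a response in the secondary ORR

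*Combined protocol and SAP*

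**What the plan says.** - **On-study steroids (6.2).** "Erythropoietin, blood products, anti-emetics, steroids, and transfusions may be administered at the discretion of the Investigator based on established criteria". The established criteria are not defined, and nothing links steroid dose to scan dates. The same section states that "All concomitant medications and treatments will be documented on the appropriate case report form".
- **Steroids at entry (4.1, criterion 9).** "Subjects with CNS disease currently taking steroids must have been on a stable dose of steroids for 2 weeks prior to their biopsy". Item 14 of 5.2 asks for "Concomitant medications/therapies including documentation of steroid use and dose".
- **Response (7.3).** RECIST 1.1 is used for solid tumors, with no separate brain-tumor criteria. PR is "At least a 30% decrease in the disease measurement, taking as reference the disease measurement done to confirm measurable disease at study enrollment", with no new lesions and no progression of non-target measurable lesions. CR, VGPR, SD and PD likewise depend on lesion size and new lesions. Steroid dose appears in none of them.
- **Responder (synopsis, Criteria for Evaluation).** "A subject will be defined as a responder if CR/PR is observed at any time of the treatment".
- **Analysis (12.4).** Response rates with exact 95% intervals, Kaplan-Meier PFS by stratum, and exploratory Cox models. No steroid-aware analysis is planned. The synopsis and Section 8 add a comparison of ORR and PFS between the first and second 100 patients.

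**The concern.** ORR and PFS are the secondary measures of the activity of the chosen regimens. In a child with a CNS lesion, a supportive drug whose dose may change between baseline and the response scan could move the measured diameter. The scoring rule cannot tell that change from an effect of the regimen. The problem can run both ways: an increase could produce a PR or delay PD, and a reduction could produce a size-only PD.

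At stake are the brain-tumor ORR (stratum 2, 50 of 200 evaluable subjects), duration of response and PFS in the same children, and the non-randomized cohort comparison. Section 1.2 says that treatments for relapsed CNS tumors often yield few or no responders, so a handful of misattributed responses could make up much of the observed rate.

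**Working it through.** **The plan's own calculation.** The only design figures are for the two-stage feasibility rule in Section 8. P(X ≤ 5 | n = 9, p = 0.50) = 382/512 = 0.746, and at p = 0.75 it is 0.166. Both match the text. The full rule (5/9, then 10/16) has type I error 0.088 and power 0.753, within the stated 10% and 75%. Feasibility does not involve response, so none of this depends on steroid scoring.

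**Does any other provision catch a steroid-driven PR?**

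1. *Entry stability.* It covers the 14 days before biopsy. Screening imaging may be up to 21 days before biopsy (5.2), so the baseline scan can fall up to 21 − 14 = 7 days before the stable window opens. Stored tissue may be up to 12 weeks old at enrollment, so the window can also be long past.
2. *Repeat baseline scans (5.2).* These are required after a bridging cycle or a gap of more than 28 days. The attached condition is hematologic recovery, not steroid dose.
3. *Review of responders (7.3).* It uses marrow and urinary catecholamines, which do not address a brain lesion.
4. *Extramural image review (7.1).* It is optional, and the plan does not say that reviewers see steroid dose.
5. *Analysis (12.4).* Nothing is specified.

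So the rule as written scores the PR.

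**Worked case (assumed diameters).** Baseline 40 mm falls to 28 mm after a steroid increase: (40 − 28)/40 = 30%, a PR. On reduction it measures 34 mm: (34 − 28)/28 = 21% and +6 mm over nadir, which meets the PD definition in 7.3. The PFS paragraph of 7.3 refers instead to screening measurements. Against 40 mm, 34 mm is not an increase, so the effect on PFS depends on which reference is used.

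**Size per event.** One extra PR adds 1/50 = 2 points to the stratum 2 ORR, 1/200 = 0.5 points to the pooled ORR, and 1/100 = 1 point to the ORR of one cohort in the comparison. Section 12.4 includes compassionate-access patients in the secondary analysis. If they enlarge the denominators, each event weighs slightly less.

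**Illustration with counts (assumed; exact 95% CI, n = 50).**
- 2 true responders: 4% (0.5 to 13.7%)
- plus 3 steroid-driven PRs, 5/50: 10% (3.3 to 21.8%)
- plus 5 steroid-driven PRs, 7/50: 14% (5.8 to 26.7%)

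**Illustration with rates (assumed).** Let t be the true ORR and f the share of non-responders with a steroid-driven shrinkage of at least 30%. Observed ORR = t + (1 − t)f, so the rise is (1 − t)f. For t and f each from 5% to 20%, the rise in stratum 2 runs from 0.80 × 0.05 = 4 points to 0.95 × 0.20 = 19 points. In the pooled 200 it is a quarter of that, 1.0 to 4.75 points. The documents give neither t nor f.

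**The case against.** Several objections stand in whole or in part.

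- *Steroids are not unrestricted.* Section 6.2 ties them to established criteria, and use is recorded on the CRF. This is correct. But the criteria are undefined and no scoring or analysis rule uses the record.
- *The entry rule need not show that the plan sees steroids as a confounder of response.* A reader might infer that from criterion 9. The documents do not say so: the rule is tied to the biopsy and sits beside a hydrocephalus condition, so it may be about clinical stability. The point does not need that inference.
- *The documents never say that steroids change lesion diameter.* True. That step is an assumption, as is every count and rate above, and the illustrative intervals overlap widely.
- *Only secondary, descriptive endpoints are affected.* True. No threshold or go/no-go rule hangs on ORR or PFS.
- *Regimen steroids can be told apart from supportive ones.* Dexamethasone, prednisolone and cortisone are in Appendix III, so either role is possible. The treatment-specific memo should separate them, although no analysis rule says so.
- *A prospective-only correction would harm the cohort comparison.* This is the strongest practical objection. At Amendment 3.0, 100 subjects were already enrolled, and a rule applied only to later subjects would define ORR differently in the two cohorts. It shapes the fix below.

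**Conclusion.** The gap is real and lies in the scoring rule of 7.3 together with the permission in 6.2. It can inflate the secondary stratum 2 ORR by 2 percentage points per misattributed PR at n = 50. It can also affect the Amendment 3.0 comparison if steroid use differs between cohorts. The total size is unknown. The conclusion assumes that steroid dose is sometimes raised between baseline and a response scan, and that this can reduce a measured CNS lesion by 30%.

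Two stronger readings go too far. One is that the brain-tumor ORR will be materially wrong, or that cohort drift has occurred: the documents contain no steroid-use data by subject or cohort. The other is that the trial's main conclusion is compromised: feasibility counts process steps through one completed cycle and does not use response. The change is worth making because it is cheap and protects the interpretation of secondary results, not because it rescues the design.

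**What to change.** In 7.3 and 12.4, for subjects whose measured lesions are in the CNS:

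1. Report the ORR as now defined alongside a steroid-conditioned ORR. In the latter, CR, VGPR or PR counts only if the supportive steroid dose at that scan is not above the dose at the baseline scan. Otherwise that scan is scored no better than SD.
2. Apply the same rule to both cohorts. For the first 100 subjects, take doses retrospectively from the concomitant-medication CRF, and report scans with unknown dose as a separate category.
3. Record steroid dose at each scan date from now on. The present record may miss it. The Table of Procedures leaves concurrent medications blank on days 8, 15 and 22, although 5.3.2 to 5.3.4 list them. Scans fall in the last week of a cycle, and the next day 1 may come up to 14 days after the cycle ends, so the two can be about 7 + 14 = 21 days apart.
4. Identify steroids chosen as regimen agents from the treatment memo and show those subjects separately.
5. For PFS, flag and count size-only PDs that follow a steroid reduction, but do not delete or censor them. PD ends study therapy (11.1), and an end-of-study assessment is asked for only when possible (7.1). Removing these events would be informative and would bias PFS upward.

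**Cost.** Some wording, one CRF field and a retrospective look-up. A few genuine responses under raised steroids will not count in the conditioned ORR, which is why both versions are reported. First-cohort dose data may be incomplete. Steroid prescribing is unchanged.
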